### **6.2.4 Clinical Laboratory Abnormalities and Other Abnormal Assessments**

Abnormal laboratory findings (e.g., clinical chemistry, hematology, coagulation and urinalysis) or other abnormal assessments (e.g., ECGs, vital signs) that are judged by the Investigator (or medically qualified designee) at the site as clinically significant or result in clinical sequelae will be recorded as AEs if they meet the definition of an AE (refer to **6.2.1 Adverse Event**). Clinically significant abnormal laboratory findings or other abnormal assessments that are detected during the study or are present at baseline and significantly worsen following the start of the study will be reported as AEs. The Investigator will exercise his or her medical and scientific judgment in deciding whether an abnormal laboratory finding or other abnormal assessment is clinically significant.

### **6.2.5 Serious Adverse Events Related to Study Participation**

A SAE considered related to study participation (e.g., procedures, invasive tests, a change in existing therapy), even if it occurs during the pre- or post-treatment period, will be reported.

## 6.3 ADVERSE EVENT REPORTING

### 6.3.1 Reporting Period

Subjects will be evaluated for safety if they have received any treatment. Any preexisting conditions or signs and/or symptoms present in a subject prior to the start of the study (i.e., before informed consent) should be recorded as medical/surgical history. All AEs occurring after informed consent and on or before the final visit must be reported as AEs; only AEs that occur post-dose will be considered treatment-emergent. All AEs must be recorded irrespective of whether they are considered drug related.

### 6.3.2 Adverse Event Collection

All AEs reported by the subject or noted in the medical record during the course of the study will be evaluated. At each encounter, subjects will be asked non-leading questions to determine the occurrence of AEs. AEs will be elicited using a standard non-leading question such as “How did you feel since last visit?” In addition, any signs or symptoms will be observed.

Adverse events may be collected from:

- The subject’s positive response to questions about their health
- Symptoms spontaneously reported by the subject
- Clinically relevant changes and abnormalities observed by the Investigator (e.g. local and systemic tolerability, laboratory measurements, results of physical examinations)

When an AE occurs, it is the responsibility of the Investigator to review all documentation relative to the event, including, but not limited to progress notes, laboratory, and diagnostic reports. The Investigator will then ensure that all relevant information regarding an AE is expediently recorded in accordance with the eCRF guidelines, including proper coding of the event term per the Medical Dictionary for Regulatory Activities (MedDRA). Investigators should be mindful of expedited reporting requirements for SAEs (refer to 6.5 Expedited Reporting of Serious Adverse Events). The Investigator will attempt to establish a diagnosis of the event based on signs, symptoms, and/or other clinical information. In all cases, when available, the diagnosis should be reported as the AE and not the individual signs/symptoms. It is not acceptable for the Investigator to send photocopies of the subject’s medical records to the Sponsor in lieu of completion of the appropriate AE eCRF pages.

The Investigator or designee will record all AEs in the source document as well as in each subject’s eCRF with information about:

- Adverse event and relevant clinical findings
- Time/date of onset
- Time/date of recovery or current status of adverse event

- Intensity/severity
- Action taken on study treatment
- Other action taken to treat the event
- Relation to study treatment
- Seriousness of the AE

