### **7.4.1 Source Documentation Reporting Requirements**

Images and corresponding reports for any brain imaging completed as part of standard of care treatment for any enrolled subject throughout the duration of the study (i.e. initial presentation through withdrawal) will be submitted to the CRO. In addition, it may be necessary from time to time to submit other source documents to the CRO or Sponsor to allow for timely safety discussions (i.e. expedited reporting of SAEs).

All source documents submitted to the Sponsor or its representatives, including imaging and reports, must be de-identified according to local and federal confidentiality requirements and identified by the subject number.

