#### **8.3.2.1 Adverse Events/Serious Adverse Events**

Adverse events (AEs) will be coded using the Medical Dictionary for Regulatory Activities (MedDRA®) and data will be summarized by System Organ Class (SOC) and Preferred Term (PT). The number and percent of subjects reporting each AE will be summarized for each treatment group and overall. A subject with two or more AEs within the same level of summarization (i.e., SOC or PT) will be counted only once in that level using the most severe (i.e., highest severity/grade) event or most related (for the relationship to study treatment table). Percentages will be based on the number of subjects in the Safety Population within each treatment group. The number of AEs reported will also be presented.

Treatment-emergent AEs (TEAEs) are defined as pre-treatment existing conditions that worsen after study treatment administration, or events that occur during the course of the study during or after administration of study treatment. Only TEAEs will be included in the AE summary tables which will present data by treatment group. In the case of a missing AE start date or stop date, the most conservative approach will be followed.

An overall summary of AEs will be produced including the number of TEAEs; the number and % of subjects reporting at least one: TEAE, serious TEAE, grade 3 or higher TEAE, TEAE related to study treatment (possible, probable), serious TEAE related to study treatment, grade 3 or higher TEAE related to the study treatment, TEAEs by maximum severity and TEAEs by maximum relationship, as appropriate.

Additional AE tables will be generated as follows, as appropriate:

- Overall TEAEs by SOC and PT
- TEAEs by Maximum Severity
- TEAEs by Maximum Relationship to Study Treatment
- Treatment Emergent SAEs

- TEAEs with Grade 3 or Higher
- Study Treatment Related TEAEs by SOC and PT
- Study Treatment Related TEAEs by Maximum Severity

A by-subject AE data listing, including verbatim term, MedDRA SOC and PT, severity, outcome and relationship to study treatment, will be provided. A separate listing will be generated for SAEs.

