## **9 RISK/BENEFIT ANALYSIS**

### **9.1 POTENTIAL RISKS**

Previous pre-clinical and clinical studies have shown DM199 to be generally safe and well-tolerated, with postural hypotension as a drug-related side effect demonstrated at high doses (refer to **1.2 Nonclinical Summary** and **1.3 Clinical Summary**). The effects of the study treatment on human pregnancy and the unborn fetus are unknown.

Refer to the Investigator's Brochure for full investigational product information including a comprehensive listing of known safety information.

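### MedDRA coding is assigned to the sites and no planned table counts subjects with hypotension, the effect the protocol calls expected, so an excess can be spread over several rows

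*Combined protocol and SAP*

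**What the plan says.** **Who codes.** Section 6.3.2 has the investigator ensure that the information on each event is recorded, "including proper coding of the event term per the Medical Dictionary for Regulatory Activities (MedDRA)". Section 8.3.2.1 says only that "Adverse events (AEs) will be coded using the Medical Dictionary for Regulatory Activities (MedDRA)". It names no coder, dictionary version or central review. Section 2.3 allows up to twelve sites.

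**How events are grouped.** Under section 8.3.2.1, "data will be summarized by System Organ Class (SOC) and Preferred Term (PT)". A subject with several events in one SOC or PT "will be counted only once in that level using the most severe" event. Further tables cut the same events by severity, seriousness, Grade 3 or higher and relationship (for example "TEAEs by Maximum Relationship to Study Treatment"). The section also promises a listing: "A by-subject AE data listing, including verbatim term, MedDRA SOC and PT, severity, outcome and relationship to study treatment, will be provided".

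**What effect is expected.** Section 1.1 reports hypotension at very high doses as expected from the mechanism. Section 1.3 reports postural hypotension. Section 9.1 describes DM199 as generally safe and well tolerated, "with postural hypotension as a drug-related side effect demonstrated at high doses". Section 4.5 names severe hypotension among the reasons for permanent discontinuation.

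**How results are judged.** AE incidence is listed first among the primary safety endpoints (sections 2.2.1 and 8.2.1). Section 8.3 plans descriptive statistics without formal comparison of the arms and leaves further methods to a separate SAP, which is not in the text supplied.

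**The concern.** In a trial without formal comparisons, the way the rows of the AE table are formed largely is the analysis of the primary AE endpoint. Two features can fragment those rows.

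- Section 6.3.2 is the only text that says who is responsible for coding. With 66 subjects and up to twelve sites, the average is 66/12 = 5.5 subjects per site. Different coders can give similar events different terms.
- Even with consistent coding, clinically related events such as hypotension, postural hypotension, dizziness on standing or syncope may fall under different PTs and in different SOCs. No planned table counts the subjects with at least one of them. PT rows cannot simply be added, because a subject with two terms appears in both.

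What is at stake is whether the safety tables can show an imbalance in an effect the sponsor already anticipates. At 33 per arm, a moderate excess can become several rows of one to three subjects, each unremarkable alone.

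**Working it through.** **Inputs from the protocol.** 66 enrolled, 1:1, 33 per arm, 10% drop-out, 60 completers (section 8.1.2); up to twelve sites (section 2.3).

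**The plan's own figure.** 60 × 1.10 = 66, and 30 × 1.10 = 33 per arm, as stated. Dividing instead gives 60/0.90 = 66.7, so 67. The difference is immaterial here. No alpha, power or effect size is given.

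**Assumed inputs.** The documents give no expected hypotension rate and no term list. The rates, the number of PTs (k), equal use of the PTs, one term per affected subject, and an excess of 4 as a visible signal are all assumptions.

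**Method.** Let a and b be the affected subjects on DM199 and placebo, with a ~ Bin(33, p1) and b ~ Bin(33, p0).

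- One pooled row: P(a − b ≥ 4) = sum over all a, b with a − b ≥ 4 of Bin(a; 33, p1) × Bin(b; 33, p0).
- k rows: each affected subject is assigned at random to one of k equally likely PTs, giving A_j and B_j. The quantity is P(max over j of (A_j − B_j) ≥ 4), from 400,000 simulations.

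**Expected counts at 20% against 5%.** Pooled: 33 × 0.20 = 6.6 against 33 × 0.05 = 1.65. Over three PTs: 6.6/3 = 2.2 against 1.65/3 = 0.55 per row.

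**Chance that some row shows at least 4 more DM199 subjects**

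| Assumed rates | Pooled | Two PTs | Three PTs |
|---|---|---|---|
| 10% vs 3% | 26% | 11% | 5% |
| 15% vs 5% | 46% | 27% | 16% |
| 20% vs 5% | 71% | 50% | 34% |
| 30% vs 10% | 84% | 73% | 60% |

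**Sensitivity.**

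- Uneven split: at 20% vs 5%, a 60/20/20 split over three PTs gives 43%, against 71% pooled.
- Stricter threshold: for an excess of at least 5 at 20% vs 5%, the values are 56% pooled, 28% over two PTs and 13% over three.
- False signals: with both arms at 5%, an excess of 4 or more appears in 2.4% of trials pooled and in about 0.4% over three PTs.
- Limits of pooling: exact two-sided Fisher power for the pooled row is only 12% at 15% vs 5% and 29% at 20% vs 5%. Pooling makes the count readable; it does not make the trial well powered.

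**Example.** Six against two subjects in one row could appear as 2 vs 1, 2 vs 1 and 2 vs 0.

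**The case against.** The case on the other side is substantial.

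- **Fragmentation is not established.** Section 6.3.2 tells investigators to report the diagnosis, when available, rather than signs and symptoms. This works against scattering hypotension into dizziness or syncope. The wording of section 8.3.2.1 is compatible with central coding, and the CRO procedures (section 8.3) and data management plan (section 7.1) may require it. The verbatim terms stay in the listing, so recoding is possible. This stands as mitigation, but no reviewed text requires central coding or review.
- **SOC rows recombine some PTs.** At assumed rates of 24% vs 6%, the chance is 81% pooled and 34% over four equal PTs, but 52% if two of the four share a SOC, and 71% under a 50/30/10/10 split with the top two in one SOC. These figures ignore unrelated events in that SOC. So the loss can be much smaller than an even split suggests, though pooling is better in every case examined.
- **Blood pressure has its own route.** It is a primary safety measure, taken after dosing (section 5.6) and summarised by arm with change from baseline (section 8.3.2.3). A reader might infer that the trial could miss hypotension altogether; the documents do not support that. The remaining gap is that readings are seated only, so a postural effect may be missed.
- **The assumed rates may be high.** Section 1.3 reports one related postural hypotension among 37 diabetes patients, placebo included, at 15 or 30 µg/kg subcutaneously; section 4.1 gives 3 µg/kg subcutaneously here. The populations differ, but the rates in the table remain illustrations.
- **Further detail is deferred.** The separate SAP may add term groups, and a DSMB reviews safety (section 6.1). Neither commits the sponsor to a hypotension count.

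A reader might also extend the point to intracranial haemorrhage, because section 7.4.1 sends the CRO "Images and corresponding reports for any brain imaging completed as part of standard of care treatment for any enrolled subject". The documents do not support that extension. They do not name haemorrhage as a risk of DM199, no study scan is scheduled, so ascertainment would be incomplete, and symptomatic status cannot be read from an imaging report alone.

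**Conclusion.** The point holds in limited form. Responsibility for coding is given to investigators, no central coder or dictionary version is named, and medical grouping stops at SOC and PT. As a result, the effect the protocol calls expected can be spread over several rows, and no planned table counts the subjects who had it.

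It would go too far to say that events will be split, or that SOC and PT are the sole tabulations. Severity, relationship, seriousness and grade tables are planned too, although none of them adds up one medical concept.

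On size, under assumed rates of 15–20% vs 5% and two or three equally used PTs, fragmentation lowers the chance of a visible excess from 46–71% to 16–50%. The direction was the same in every scenario run; the amount depends on rates and term patterns that the documents do not give. The change is worth making because AE incidence is a primary endpoint and the remedy is cheap.

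**What to change.** 1. **Section 6.3.2:** have sites record the verbatim diagnosis. Have the CRO code all events centrally with one stated MedDRA version, with blinded medical review of the coding before database lock. Name the coder and version in section 8.3.2.1 as well.
2. **Section 8.3.2.1, or the separate SAP:** add a by-arm table of subjects with at least one TEAE in a hypotension/blood-pressure-decrease term group. Fix the term list before unblinding. Report counts, percentages and 95% confidence intervals, and keep the SOC and PT tables as planned.

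**Cost.** Changes of wording, one extra table and coding moved to the CRO. Treatment, visits and data collected do not change. The term list must be agreed before lock, and false signals rise slightly (from about 0.4% to 2.4% in the illustration with both arms at 5%). The pooled row should be read as descriptive, in line with section 8.3.

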### **6.3.3 Adverse Event Follow-up**

After the initial AE report, the Investigator is required to proactively follow each subject and provide further information to the Sponsor on the subject's condition as deemed appropriate. All AEs will be followed until resolution, until the condition stabilizes, until the event is otherwise explained, or until the subject is lost to follow-up. Once resolved, the appropriate AE eCRF page and SAE report form (if applicable) will be updated. The Investigator will ensure that follow-up includes any supplemental investigations as may be indicated to elucidate the nature and/or causality of the AE. This may include additional laboratory tests or investigations, histopathological examinations, or consultation with other health care professionals. In the event of a fatal outcome in an SAE, the Investigator will attempt to obtain postmortem findings, including histopathology and provide all additional information in a follow up SAE report. New or updated information will be recorded on a new SAE report form marked as a follow-up with the appropriate follow-up number added to the report. The follow-up report will be signed and dated by the Investigator or medically qualified designee.

### **6.3.4 Pregnancy Reporting**

If a subject inadvertently becomes pregnant during the study the pregnancy will be reported to the Sponsor via the Pregnancy eCRF. If the pregnancy meets the definition of a SAE information will be reported using the SAE Report Form submitted within 24 hours of knowledge of the event. Study treatment will immediately cease upon learning of a subject pregnancy. The Investigator or designee will make every effort to obtain permission to follow the outcome of the pregnancy and report the condition of the fetus and newborn to the Sponsor's Medical Monitor. The Investigator or designee will attempt to contact the subject at least monthly and document the subject's status until the pregnancy has been completed or terminated. The pregnancy outcome will be reported to the Sponsor's Medical Monitor (or designee) without delay, or within 24 hours if the outcome is a serious adverse event (e.g., death, abortion, congenital anomaly, or other disabling or life-threatening complication to the mother or newborn).

If a male subject impregnates his female partner the pregnancy should be reported to the Sponsor's Medical Monitor and followed as described above.

### 6.3.5 Post-study Adverse Events

A post-study AE is defined as any event that occurs outside of the AE reporting period defined in **6.3.1 Reporting Period**.

Investigators are not obligated to actively seek AEs in former study subjects. However, if the Investigator learns of any SAE, including death, at any time after a subject has been discharged from the study, and he/she considers the event reasonably related to the investigational product, the Investigator will promptly notify the Sponsor.

## 6.4 EVALUATION OF ADVERSE EVENTS

### 6.4.1 Assessment of Intensity

Adverse events and other symptoms will be graded according to National Cancer Institute's Common Toxicity Criteria for Adverse Events version 4.03 (CTCAE v4.03).

The Investigator or medically qualified designee will make an assessment of intensity for each AE reported during the study. The assessment will be based on the Investigator's (or medically qualified designee's) clinical judgment. The intensity should be assigned to one of the following categories:

**Table 4: CTCAE Grading**

Grade	Clinical Description of Severity
0	No Change from Normal or Reference Range (This grade is not included in the Version 4.0 document but may be used in certain circumstances.)
1	MILD Adverse Event Asymptomatic or mild symptoms; clinical or diagnostic observations only; intervention not indicated.
2	MODERATE Adverse Event Moderate; minimal, local or noninvasive intervention indicated; limiting age-appropriate instrumental activities of daily living (ADL)*.
3	SEVERE Adverse Event Severe or medically significant but not immediately life-threatening; hospitalization or prolongation of hospitalization indicated; disabling; limiting self-care ADL**.
4	LIFE-THREATENING OR DISABLING Adverse Event Life-threatening consequences; urgent intervention indicated.
5	DEATH RELATED TO Adverse Event

\*Instrumental ADL refer to preparing meals, shopping for groceries or clothes, using the telephone, managing money, etc.

\*\*Self-care ADL refer to bathing, dressing and undressing, feeding self, using the toilet, taking medications, and not bedridden.

An AE that is assessed as severe should not be confused with a SAE. Severity is a category utilized for rating the intensity of an event; and both AEs and SAEs can be assessed as severe.

If an AE worsens in intensity, it should be recorded as a new AE. If an AE gets milder in intensity, it continues as the first report until the subject is recovered.

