#### 4.5 DOSE DELAYS AND MISSED DOSES

Study treatment must be withheld for any Grade  $\geq 3$  injection-site reaction or investigational product related AE. The delayed treatment may be resumed once the AE has resolved to Grade 0 or 1. However, subsequent injections must remain on schedule. A minimum of  $72 \pm 2$  hours must elapse between injections. If the dose cannot be given within the scheduled window, then the injection must be missed. If  $\geq 2$  doses are missed due to AEs, then DM199 should be permanently discontinued.

If study treatment is delayed, all required testing that are scheduled to occur on dosing days must be repeated at the time treatment resumes. This includes: body weight, height, and BMI calculation; vital sign measurements; urine sample for KLK1 concentration, and clinical labs.

Study treatment should be permanently discontinued for any of the following reasons:

- Dosing is delayed for more than 6 days
- Any of the following adverse drug reactions (ADRs):
  - Any life-threatening (Grade 4) ADR
  - Severe (Grade 3) hypotension requiring sustained IV fluids replacement
  - Severe (Grade 3) hypoglycaemia
  - Severe (Grade 3) infusion-related reactions
  - Severe (Grade 3) ADR that recurs
- Observation of any other toxicities that in the opinion of the Investigator suggests that there may be a significant increase in either the incidence or severity of any events with study treatment. In this case, the Investigator will contact the Sponsor's Medical Monitor to conduct a review of all safety data.

Dose reduction of study treatment is not allowed.

Any study treatment delays or missed doses must be documented in the electronic case report form (eCRF) and in the subject's study chart, including a detailed reason for the change.

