## 6.2 DEFINITIONS

### 6.2.1 *Adverse Event*

An adverse event (AE) is any untoward medical occurrence in a subject or clinical investigation subject administered a pharmaceutical product and which does not necessarily have to have a causal relationship with the treatment. An AE can therefore be any unfavorable and unintended sign (including an abnormal laboratory finding), symptom, or disease temporally associated with the use of a medicinal (investigational/experimental) product, whether or not related to the product (Refer to International Conference on Harmonization [ICH] E2A: Clinical Safety Data Management: Definitions and Standards for Expedited Reporting, 27 October 1994).

Treatment-emergent AEs will be defined as AEs with an onset after administration of the study treatment, or when a preexisting medical condition increases in severity or frequency after study treatment administration.

Adverse Events (AEs) will not include:

- A medical or surgical procedure such as surgery, endoscopy, tooth extraction, or transfusion (although the condition that leads to the procedure may be an AE)
- A pre-existing disease or condition present at the start of the study that does not worsen during the study
- Any situation where an untoward medical occurrence has not occurred (for example, hospitalizations for cosmetic elective surgery or social admissions)
- An overdose of either the investigational product or a concurrent medication without any resulting signs or symptoms

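### Table 4 places disability in both Grade 3 and Grade 4, so a disabling AE that is neither life-threatening nor urgent can be graded either way (minor)

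*Combined protocol and SAP*

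**What the plan says.** Section 6.4.1 names CTCAE v4.03 as the grading standard, leaves the assessment to the clinical judgment of the investigator or a qualified designee, and then points to Table 4: "The intensity should be assigned to one of the following categories".

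In Table 4, Grade 3 is for events without an immediate threat to life, and its criteria include "hospitalization or prolongation of hospitalization indicated; disabling; limiting self-care ADL". The Grade 4 entry, label and description together, is "LIFE-THREATENING OR DISABLING Adverse Event Life-threatening consequences; urgent intervention indicated".

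The grades are used in two places. Section 4.5 stops treatment permanently for "Any life-threatening (Grade 4) ADR". For other related events of Grade 3 or above it withholds treatment: "The delayed treatment may be resumed once the AE has resolved to Grade 0 or 1". Section 8.3.2.1 summarises treatment-emergent AEs by maximum severity, counting each subject once at the highest grade. AE severity is part of the primary safety endpoint (section 8.2.1).

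**The concern.** A severity scale should give each event one grade. Here the word *disabling* belongs to two adjacent grades, and neither section 6.4.1 nor Table 4 says whether the label or the description prevails. Two raters who agree on the clinical facts could record different grades. The protocol allows up to twelve sites (section 2.3), so different readings are plausible.

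What is at stake is the consistency of the severity data behind a primary endpoint, in the outputs that separate Grade 3 from Grade 4. Because section 4.5 also treats the two grades differently, dosing decisions need checking too.

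**Working it through.** The protocol gives no figure to reproduce. The check compares the texts and then traces where a difference would show.

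**1. One test event against each text.** Take an AE that is new or worsened, disabling, not life-threatening and not in need of urgent intervention.

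- Grade 3 description: met, since disability is listed and there is no immediate threat to life.
- Grade 4 description: not met, since it names only threat to life and urgent intervention.
- Grade 4 label: met, through its second limb.
- Section 4.5: Grade 4 is glossed as life-threatening, with no mention of disability.
- Table 5 (injection-site events): the Grade 4 column is headed as potentially life-threatening, with no mention of disability. For pain and induration, limits on self-care sit at Grade 3.

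Four of the five texts agree, and the Grade 4 label stands alone.

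**2. Subject counts.** Section 8.3.2.1 reports maximum severity in the overall summary, in the table for all treatment-emergent AEs and in the table for treatment-related ones. In these a subject can move from Grade 3 to Grade 4. The number of subjects at Grade 3 or above cannot change, because both readings are at least Grade 3.

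**3. Size per subject.** Inputs: up to 66 enrolled, randomised 1:1 (section 8.1.2), so 66/2 = 33 per arm. Treating all 33 is an assumption, because 33 is the enrolment ceiling and not the treated number. The documents give no frequency for such events, so the affected numbers below are assumed.

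- 0 subjects: 0/33 = 0 points
- 1 subject: 1/33 = 3.0 points
- 2 subjects: 2/33 = 6.1 points

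With 30 treated per arm, one subject would be 1/30 = 3.3 points.

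**4. Event counts.** The text under Table 4 says that an AE that worsens in intensity is entered as a new AE. Suppose a Grade 3 event later becomes disabling. Under the description it stays Grade 3 and remains one record. Under the label it rises to Grade 4 and becomes two. Section 8.3.2.1 also presents numbers of AEs, so event counts can differ by one for each such case, including events at Grade 3 or above.

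**5. Stopping treatment.** If the test event is a related AE and is graded 3, section 4.5 still stops treatment permanently in any of these cases:

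- it is a named Grade 3 reaction (hypotension needing sustained IV fluids, hypoglycaemia, infusion-related reaction);
- it returns: "Severe (Grade 3) ADR that recurs";
- the delay is long: "Dosing is delayed for more than 6 days";
- two or more doses are missed because of AEs.

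Doses are 72 hours apart. If the event starts just before a scheduled dose, a second dose falls due after about 72 hours. If it starts just after a dose, the second falls due after 2 × 72 = 144 hours, or 6 days. So the grade could matter only for a first related event, outside the named types, that settles to Grade 0 or 1 within roughly 3 to 6 days. Even then the stopping rule's own words require threat to life, so the difference arises only if someone acts on the grade number and ignores those words.

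**The case against.** The strongest reply is that the documents nearly settle the matter. The table column holds clinical descriptions of severity. Read by description, the test event is Grade 3 and fails Grade 4, and section 4.5 and Table 5 agree. CTCAE v4.03 is the named standard, and a careful rater would usually reach Grade 3. All of that stands, and it is why the point is minor and the correction is not in doubt. It does not remove the conflict. Raters are sent to the printed categories, the label is part of the category, and no order of precedence is given. Whether CTCAE v4.03 itself settles the point cannot be checked from these documents, so nothing here rests on it.

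Several stronger readings are tempting, and the documents do not support them.

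- *Disability from the index stroke would be misgraded on a large scale.* Section 6.2.1 excludes this from AEs: "A pre-existing disease or condition present at the start of the study that does not worsen during the study". Only new or worsened events are affected.
- *Recurrent stroke is the typical case.* It is a weak example. Section 9.2 describes stroke treatments limited to hours after onset, so urgent intervention may be indicated. The Grade 4 description would then apply without the disputed label.
- *Serious events would be missed.* Lasting or significant disability is a seriousness criterion of its own (section 6.2.2), and the protocol separates severity from seriousness.
- *Subjects would be wrongly taken off treatment.* Step 5 of the working shows that this is close to nil.
- *The comparison of arms would be biased.* Site raters are blinded (section 5.3) and no formal comparison is planned (section 8.3). The concern is inconsistency between raters.

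**Conclusion.** The point holds as a minor internal inconsistency: Table 4 is wrong as written. A new or worsened AE that is disabling, not life-threatening and not in need of urgent intervention can be recorded as Grade 3 or Grade 4.

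The overlap can shift a subject between these grades in the maximum-severity summaries, by about 3 percentage points per subject if 33 per arm are treated. It can also add an AE record when a Grade 3 event becomes disabling. A reader might infer that every count at Grade 3 or above is safe. That is true of subjects but not of events.

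The existence of the overlap rests on the protocol's wording alone. The size rests on two assumptions: the number treated per arm, and the number of such events, which is unknown and probably small.

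**What to change.** In Table 4, delete *OR DISABLING* from the Grade 4 label so that it reads *LIFE-THREATENING Adverse Event*. Leave the Grade 3 description unchanged. Nothing is lost, because disability stays in Grade 3 and remains a seriousness criterion in section 6.2.2.

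Make a brief blinded check of events already graded 3 or 4, including any that were re-entered as new AEs only because they became disabling. It should be finished before database lock.

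The cost is two words in one label plus that check, with no new data, visits or staff. Amendments need ethics approval at each site before adoption there (section 13.6), at up to twelve sites. The edit should therefore go into the next amendment and does not justify one of its own.
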